8.11. Adverse Events

If patients experience an adverse event during the course of the study, we will conduct an assessment, complete an Adverse Event form, and follow the adverse event reporting system as required by our IRB and NIH regulations. We will assess Adverse Events at each intervention session.

Adverse events are defined as any untoward or unfavorable medical occurrence in a human subject, including any abnormal sign (for example, abnormal physical exam or laboratory finding), symptom, or disease, temporally associated with the subject's participation in the research, whether or not considered related to the subject's participation in the research.

Serious adverse events are any adverse event temporally associated with the subject's participation in research that meets any of the following criteria:

- (1) results in death;
- (2) is life-threatening (places the subject at immediate risk of death from the event as it occurred);
- (3) requires inpatient hospitalization or prolongation of existing hospitalization;
- (4) results in a persistent or significant disability/incapacity;
- (5) results in a congenital anomaly/birth defect; or
- (6) any other adverse event that, based upon appropriate medical judgment, may jeopardize the subject's health and may require medical or surgical intervention to prevent one of the other outcomes listed in this definition

At every session, we will assess both Adverse Events and Serious Adverse Events (AEs and SAEs).

All SAEs related to study participation are to be reported to the Project Manager who will report to the Study Physician (e.g., [name] [name]) within 24 hours of occurrence, and are to be reported to the UTHSC IRB immediately.

UTHSC's IRB operating procedures regarding AE's can be found here:

<https://www.uthsc.edu/research/compliance/irb/researchers/documents/adverse-event-reporting.pdf>

We do not anticipate any study related SAEs (we haven't observed treatment related SAEs in any of our studies) as our study involves an over-the-counter medication and psychosocial intervention.

A copy of the Adverse Events reporting tool is located in the Measures section.

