12.2.30. Adverse Events

What was the adverse event? _____

Onset Date: ____ / ____ / ____

End Date: ____ / ____ / ____

Was the participant using the study drug(s) at the time of the event?

- Yes
- No

Was the event related to the study intervention or study drug?

- Unrelated
- Unlikely
- Possible
- Probable
- Highly Probable

Action Taken:

- None
- Study Drug Paused
- Study Drug Discontinued
- Study Participation Paused
- Study Participation Ended

If study participation was stopped, was it stopped due to the AE?

- Yes
- No
- N/A

Was the event expected?

- Yes
 No

Severity of AE:

- Mild
 Moderate
 Severe

SAE Category:

- Not an SAE
 Inpatient hospitalization
 AE resulted in death
 Life threatening
 Permanent or severe disability
 Congenital anomaly
 Treatment to prevent an above serious event

Outcome:

- Completely recovered
 Recovered with sequelae
 Condition improving
 Condition present and unchanged
 Condition deteriorated
 Death due to this AE
 Other
-
-
-

Narrative/Comments:

Staff Initials: _____

MD Check Off Initials _____

Date: ____ / ____ / ____

- Approved
 Needs QC

MD Additional Information Needed:

QC Completed By _____
QC Date: ____ / ____ / ____

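### The SAE Category options on the adverse-event form do not match the six SAE criteria in section 8.11, most clearly for disability

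*Protocol*

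**What the plan says.** Protocol section 8.11 gives the only definition of a serious adverse event in the manual. It lists six criteria, any one of which suffices. Three matter here: the event "requires inpatient hospitalization or prolongation of existing hospitalization"; the event "results in a persistent or significant disability/incapacity"; or, in medical judgment, it may put the participant's health at risk and "may require medical or surgical intervention to prevent one of the other outcomes listed in this definition". The section also says: "A copy of the Adverse Events reporting tool is located in the Measures section".

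That tool is the form in section 12.2.30. Its SAE Category item is a closed list of seven options: one for a non-serious event and six for serious events. The options corresponding to the three criteria above read "Inpatient hospitalization", "Permanent or severe disability" and "Treatment to prevent an above serious event". The form neither repeats the section 8.11 definition nor refers back to it. It does have a free-text event description, a narrative field, a physician check-off and a quality-control sign-off.

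**The concern.** A definition and the form that records it should agree. Section 8.11 has adverse events and SAEs assessed at every session, and those sessions are run by interventionists (sections 4.3.4 and 8.6). They complete a fixed list in which some labels are tighter than the definition, and the list has no option for other serious events, although the Outcome item on the same form does have one. An event that meets section 8.11 but fits no label as worded could be marked as non-serious.

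What is at stake is the correct recording of a small number of safety events. Under section 8.11, an SAE related to study participation goes to the Study Physician within 24 hours and to the IRB immediately. A wrong tick at the point of recording could delay recognition that this route applies.

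**Working it through.** There is no figure in the plan to reproduce and no arithmetic beyond a count. The check sets the six criteria of section 8.11 beside the six serious options in section 12.2.30.

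| Criterion | Section 8.11 | Form, section 12.2.30 | Comparison |
|---|---|---|---|
| 1 | Death | Option for death | Same |
| 2 | Life-threatening | Option for life-threatening | Same in substance |
| 3 | "requires inpatient hospitalization or prolongation of existing hospitalization" | "Inpatient hospitalization" | Prolongation not named |
| 4 | "results in a persistent or significant disability/incapacity" | "Permanent or severe disability" | Narrower as worded |
| 5 | "results in a congenital anomaly/birth defect" | Option for congenital anomaly | Same in substance |
| 6 | "may require medical or surgical intervention to prevent one of the other outcomes listed in this definition" | "Treatment to prevent an above serious event" | Can be read more narrowly |

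Three criteria match in substance (1, 2 and 5), one is plainly narrower (4), and two are abbreviated in a way that permits a narrower reading (3 and 6): 3 + 1 + 2 = 6.

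**Criterion 4.** Persistent is a weaker condition than permanent, and significant a weaker one than severe, while incapacity is not mentioned on the form at all. A disability that lasts but resolves, and that is significant but not severe, meets section 8.11 and neither half of the form's label. The form also grades the event itself as mild, moderate or severe. Staff may read the word severe in the disability label against that scale, which would make the narrower reading more likely.

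**Criterion 3.** A participant already in hospital whose stay is lengthened by an event meets section 8.11. The form's label covers this case only if staff read it to include a stay that had already begun.

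**Criterion 6.** Section 8.11 asks whether the event may require intervention. The form's label names treatment. Read literally, an event that could have needed intervention but received none falls outside it. The label also refers back to the form's own list, so if the disability option is read literally, treatment to prevent a persistent but non-permanent disability falls outside it too.

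**Direction.** No option on the form is clearly wider than its criterion. Any misclassification caused by these labels therefore runs towards recording too few SAEs.

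**The case against.** The strongest reply is that the form does not define anything. It is a list of short labels, nothing says that they replace section 8.11, and each of the six criteria has an option on the same topic. Someone whose hospital stay is prolonged is an inpatient, so the hospitalization option is the natural tick. The preventive-treatment label can fairly be read as shorthand for criterion 6, since the form does not say that treatment must have been given. A physician check-off and a quality-control step follow, with a narrative to read. Most of this stands. It leaves disability as the one clear gap and makes the other two matters of possible reading. It does not remove the point: the check-off and quality-control fields carry no instruction to compare the tick with section 8.11.

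A reader might go further and infer that the SAE counts seen by the DSMB and the IRB would follow the narrower list. The documents do not support that. Section 8.11 ties expedited reporting to its own SAE term, not to a tick on the form. Section 9.2 says only that the DSMB reviews reports sent by the study statistician, without describing how SAEs are counted for them, and the DSMB Charter is a separate document. A reader might also try to size the problem by the effect of one event on the SAE rate in an arm of 20. That arithmetic holds for any single event and does not measure this defect. Neither the Protocol's statement of outcomes (section 3.3) nor the SAP plans a comparison of SAE rates between arms.

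**Conclusion.** The point holds as a minor internal inconsistency in safety recording. It is not a question of trial design. One of the six criteria in section 8.11 (disability) is narrower on the form as worded, and two more (prolonged hospitalization, and other medically important events) are abbreviated so that they can be read more narrowly. An affected event could be recorded as non-serious; the documents do not show that it would be.

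The conclusion rests on reading the labels as written and on section 8.11 being the governing definition. How often it would matter cannot be estimated: no event rate is given, and section 8.11 anticipates no study-related SAEs, so the number of affected events is probably very small. No feasibility, efficacy or sample-size figure changes.

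**What to change.** Reconcile section 12.2.30 with section 8.11 by using the six criteria of section 8.11, in that section's own wording, as the serious options under SAE Category, and keep the non-serious option. In particular, name prolongation of an existing stay, restore the persistent-or-significant standard and incapacity to the disability option, and restore the medical-judgment wording of criterion 6 in place of the preventive-treatment label. Make the same change in the database value list so that the paper form and the recorded code agree.

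The cost is an edit to one form and one value list. It needs no new data item or assessment and changes no clinical procedure. A slightly higher recorded SAE count is possible, because events that already meet the manual's definition would be classified as such.

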12. CM INTERVENTION SCRIPT

Hi _____. Nice to see you again. As you may remember, we check on your toxicology results to determine whether you are eligible for the number wheel.

Buprenorphine Present:

I see today you do have medication in your system. Congratulations! You are eligible for the wheel spin. As a reminder, the wheel includes gift cards ranging from \$25 to \$100. You will spin and land on a random number.

<https://pickerwheel.com/>

Buprenorphine Not Present:

I see today you do not have medication in your system. I'm sorry, but you will not be eligible for the wheel spin today.

13. BSM INTERVENTION SCRIPT

Psychosocial Intervention Session 1 (40 minutes with assessments):

Session Prep:

- a. Ensure participant has received SOBER Handout at baseline
- b. Print off blank Goals worksheet for Session 1 to fill out during session
- c. Participant should have completed the “Time Spent on Activities Worksheet” at baseline.
 - i. Have a graph of the time spent in each activity prepared and sent to the participant before the session begins
- d. Print off blank Future Event Description worksheet for Session 1 (Goals, Future Event Description) to fill out during session

1. Introduction (2 minutes)

a. Getting Permission to Record

- i. *Hi _____, is this still a good time for us to do our first session together? Great!*
- ii. *Before we get started today, I wanted to let you know all of our sessions will be recorded for the purpose of the study.*
- iii. *Do I have your permission to record this session? Thank you so much.*

b. Mandated reporting

- i. *Also, I wanted to let you know that I am a mandated reporter. That means if you let me know about any ongoing abuse, either to yourself or to someone else, or if you inform me of any intentions to harm yourself or someone else, I am obligated by law to report that. If anything like that comes up during any of our sessions, I would let you know ahead of time.*
- ii. *Do you have any questions about that?*

2. Assessment (10 minutes)

- a. Complete session one assessment forms in FileMaker.
- b. *Thank you for taking the time to answer all those questions.*
- c. *Because you finished your assessment, I will mail you that \$25 gift card. Do you prefer Kroger or Walmart? Great!*
- d. *Please allow 2-3 business days for it to arrive. If there are any issues, please don't hesitate to reach out!*

3. Build Rapport (1 minutes)

- a. *So I'd like to get to know a little more about who you are. Tell me who are the most important people in your life and one or two things you like to do – just a minute's worth of who you are.*
 - i. Wait for participant to tell you about themselves – MAXIMUM 1 minute

4. Orientation to Session (1 minute)

- a. *Thank you for telling me about yourself.*
- b. *Let me tell you about what we will be doing with our time together.*
 - i. *My overall goal is to support your treatment at the Center for Addiction Science and help you meet your goals.*
 - ii. *During our 4 sessions together, we will discuss your goals and values, identify some drug and alcohol free activities you would like to start doing, and teach you some relaxation skills.*
- c. *Do you have any questions before we start?*

- i. Answer questions
5. Goals for Treatment/Motivational Interviewing Discussion (5 minutes)
 - a. Have blank "Goals Worksheet" printed out and ready to use
 - b. Introduce Purpose
 - i. *Now first, I want to talk about your goals, both short and long term. This is to help you start to expand your thinking into the future.*
 - ii. *Why did you decide to start treatment that this time?*
 1. Things they want to accomplish as a result of being in treatment
 - c. Discuss Goals
 - i. *Thank you for sharing that with me.*
 - ii. *Now, what are your overall life goals? What would you like to accomplish?*
 1. Listen and reflect.
 2. Summarize the goals they tell you.
 3. Help them to identify at least one goal that might lead to an increase in positive drug-free activities. Many participants will naturally bring up a goal that will serve this purpose (e.g., getting in shape, meeting new people, getting a new job, improving family relationships). If they do not, you can ask them if they can think of a goal that would enrich their life in some way by enhancing their social support, enjoyment, or giving them a sense of accomplishment or purpose?
 4. *OK, great, so you would like to _____ and _____ and _____.*
 - d. Possible activity: Choose Goal and Break Down into Small Steps.
 - i. Note: Only ask them to break down a goal into smaller steps if you think that would lead to increases in positive drug-free activities.
 - ii. *Now let's choose one of those goals and really think about what it will take to reach it. How about X (goal that can lead to increased drug free activities)*
 1. *Sometimes, breaking a goal down into smaller steps helps you get started on it.*
 2. Write goal on the "Goals" worksheet (see separate page, below).
 - iii. Now let's list some short-term, specific things you need to do that will help you to reach your goal.
 1. Keep asking open-ended questions to identify 3 very specific behaviors.
 - e. Summarize
 - i. *OK, so I have that your big goal is to _____, and you will get there by doing _____, _____, and _____. Does that sound right?*
 - ii. *Now I would like to ask you, how might relapse impact this goal?*
 1. Let them answer
 2. *I see, so relapse would make it difficult to _____, but if you stay in treatment, this goal might be reachable.*
 - iii. I'm going to text you this worksheet I filled out so you can reflect on these steps we talked about and also fill in the steps for the other two goals you identified
 - iv. Send this list to the participant via text or email (if using social distancing procedures)

6. Time Spent On Activities of Daily Life (5 minutes)

- a. Participant should have completed the "Time Spent on Activities Worksheet" at baseline.

- b. Graph participant's time spent in each activity prior to session, and hand it, text it, or email it to the participant. Their answers should be in the baseline assessment in filemaker.
- c. Have this graph in front of you for this activity.
- d. Introduce Activity
 - i. *Let's change gears now and talk about the activities that are important to you in life; your priorities and core goals for yourself.*
 - 1. *You may remember that when you first came in, we asked you to fill out a questionnaire about how many hours per week you spend doing different things.*
 - 2. *I took what you wrote, graphed it out, and gave it to you before our session today.*
 - ii. *Now, if it's okay with you, I'd like to talk about these activities.*
 - 1. *One of the reasons we summarize this information is because people rarely think about how they spend their time, even though it says a lot about what they find important.*
 - iii. *So, looking across this graph at the time you spend doing different things, what stands out to you?*
 - iv. *What are some areas that you might like to change the amount of time you spend on them?*
- e. FOR THOSE WITHOUT ACCESS TO THE GRAPH
 - i. *Since you can't see the graph, let's walk through a few areas.*
 - ii. *You stated that you spend _____ hours a week with your family.*
 - 1. *How do you feel about that when you think about your goals?*
 - iii. *You spend _____ hours a week on work.*
 - 1. *How do you feel about that when you think about your goals?*
 - iv. *You spend _____ hours a week on education, hobbies, or creative activities.*
 - 1. *What kinds of things do you do?*
 - 2. *How do you feel about the amount of time you spend on this when you think about your goals?*
 - v. *You spend _____ hours a week on exercise, time in nature, or self-care.*
 - 1. *What do you think about your time spent on these activities when you think about your goals?*
 - vi. *You spend _____ hours a week watching TV or surfing the internet.*
 - 1. *What do you think about your time spent on these activities when you think about your goals?*
 - vii. *You spend _____ hours a week on religious or spiritual activity, community life.*
 - 1. *How do you feel about that when you think about your goals?*
 - viii. *You spend _____ hours a week using opioids or other drugs/alcohol.*
 - 1. *How do you feel about that when you think about your goals?*
 - ix. *You spend _____ hours a week on substance recovery and treatment.*
 - 1. *What do you think about your time spent on recovery activities when you think about your goals?*
 - x. *You spend _____ hours a week socializing with people who are supportive of your recovery.*
 - 1. *What do you think about your time spent doing this when you think about your goals?*
 - xi. *You spend _____ hours a week socializing with people who are not supportive of your recovery.*
 - 1. *What do you think about your time spent doing this when you think about your goals?*

- f. Summarize:
1. *So it sounds like you would like to spend more time _____ and also _____ because that fits with your goals of _____ and _____.*
 2. *What would keep you from changing how you spend your time?*
7. Future Events (10 minutes)
- a. Have blank "Future Event Description Worksheet" ready to use
 - b. Prepare Think Activity
 - i. *Now let's do a short thinking exercise. I am going to ask you to think specifically about positive (nice, happy) future events that could happen if you remain in recovery.*
 1. *If you are comfortable, you may close your eyes for a moment so that you can focus.*
 2. *Visualize your life 3 months into the future.*
 - ii. *Think about aspects of your life that matter to you.*
 1. *It could be how you want to grow mentally, spiritually, or physically. Think about how you would want your body and physical fitness to be, or what new skills or hobbies you may want to learn, or what new career building skills you would want to develop, or anything that gives you a sense of meaning, mission, or purpose.*
 - iii. *Pick any of these categories that are important in your life and take a minute to visualize and imagine how will feel in your life 3 months from today.*
 1. Wait about 60 seconds to let the person imagine this future event.
 - c. Describe Activity
 - i. *Now, let's talk about a specific type of positive (nice, happy) experience you are looking forward to having in your life.*
 2. *I want you to be specific about what you will be doing, who you will be with, how you imagine this one experience will feel, and the types of thoughts and emotions you have when this event takes place.*
 3. *Tell me about the future event (or events) you imagined.*
 - ii. Write down and summarize for patient.
 1. *So, if you remain in recovery, you are looking forward to _____, with _____, and this will feel _____. Did I get that right?*
 2. *That's really something to look forward to.*
8. Mindfulness-Based Adherence Promotion Intervention (5 minutes)
- a. *The last thing we'll discuss today is something called the SOBER breathing space. We're going to go over this in more detail in the weeks to come, but I want you to have an idea of what it is to help you start working through some of your triggers.*
 - b. Explain the Acronym
 - i. *SOBER stands for:*
 1. *Stop and see what happens*
 2. *Observe physical sensations and emotion regulation changes in the body*
 3. *Breathe by deliberately bringing attention to the breath*
 - a. *Describe to the participant how to breathe in through their nose and out through their mouth slowly.*
 4. *Expand awareness of the situation*
 5. *Respond mindfully (versus reacting)*

- c. Give/Send participant SOBER Handout
 - i. *I'm sending you a handout with the SOBER skillset so that you can start using this at home.*
 - d. Trigger identification
 - i. *Is there a trigger that you're worried could come up this coming week?*
 - 1. i.e., something that reminds them of opioid (or other drug) use.
 - ii. *This coming week, if _____ comes up, what would it be like to take a few minutes to SOBER?*
9. Wrap-Up (1 minute)
- a. *We talked about a lot today. I appreciate your openness.*
 - b. *To summarize:*
 - i. *It seems like you are motivated to spend more time on _____ given how important it is for you.*
 - ii. *From all the information we covered today, I'm curious about what stands out most for you?*
 - i. Allow participant to answer.
 - c. *Do you have any questions for me?*
 - d. *Let's schedule our next session together, based around your clinic visit.*
 - e. Provide participant with date and time of session.

What to send to participant after Session #1:

- 1. Completed "Goals Worksheet"
- 2. Gift Card for completed assessment

Upload into Database after Session #1:

- 1. Completed "Goals Worksheet"

Goals Worksheet

List participant's goals. If useful, break down goal into smaller steps.

Goal	Short term, specific goals
1.	1. 2. 3.
2.	1. 2. 3.
3.	1. 2. 3.

Following the session, upload this as a picture into the database under session 1 tab.

Time Spent on Activities Worksheet (uploaded at baseline as picture to database)

[figure not shown]
Instructions:

Please list how many hours EACH WEEK you spend doing each of the activities listed below.

For example, if you spend 2 hours each day playing video games, that would be 14 hours each week for the activity named “Watching TV or surfing the internet.”

	How many hours do you spend doing this activity EACH WEEK?
Family	
Work	
Education, hobbies, creative activities	
Exercise, time in nature, or self-care	
Watching TV or surfing the internet	
Religious or spiritual activity, community life	
Using opioids or other drugs/alcohol	
Substance recovery/treatment (includes counseling/medication visits and time in meetings like AA or NA)	
Socializing with people who are supportive of your recovery	
Socializing with people who are not supportive of your recovery	

Example Graph of Time Spent on Activities Worksheet

Future Event Description Worksheet

Write event below to summarize for the participant.

Following the session, upload this as a picture into the database under session 1 tab.

Handout is to be given to the participant at their baseline visit.

SOBER BREATHING SPACE

Stop and see what happens

Observe physical sensation and regulation changes in the body

Breathe by deliberately bringing attention to the breath

Expand awareness of the situation

Respond mindfully

WHEN YOU ENCOUNTER A TRIGGER, TAKE A FEW MINUTES TO PRACTICE SOBER.

Remember, this takes time and practice. Be kind to yourself.

Psychosocial Intervention Session 2 (39 minutes with assessments):

Session Prep:

- a. Goals Worksheet from session 1 that you filled out for the participant.
- b. Participant's completed Substance Free Activities Worksheet (from Baseline Assessment)
 - o Look over participant's preferred substance free activities questionnaire from baseline.
 - o Identify activities local to the participant's home or available online that could fulfill these activity needs.
 - o **Focus more** on increasing activities that include socializing with people supportive of recovery, exercise/time outdoors, and goal-directed/creative activities.
 - o **Focus less** on activities that might jeopardize recovery (time with users, activities that increase stress) or that are recovery neutral (passive leisure activities like watching TV) those should be less of a focus
 - In the case of risky activities, the clinician can ask the client how that activity would relate to their recovery goals – get the participant to make this link.
- c. ***during pandemic*** Pleasant Activities handout

1. Introduction (1 minute)

- a. Getting Permission to Record
 - i. *Hi _____, how are you today? Is this still a good time for us to do our second session together? Great! And before we get started today, do I have your permission to record this session? Thank you.*

2. Assessment (10 minutes)

- a. Complete session two assessment forms in FileMaker.
- b. *Because you finished your assessment, I will mail you that \$25 gift card. Do you prefer Kroger or Walmart? Please allow 2-3 business days for it to arrive. Thanks for getting the assessment completed today.*

3. Continue to Build Rapport (2 minutes)

- a. *Tell me how you've been since the last time we spoke.*
- b. Wait for participant to tell you how they are.

4. Orientation to Session (1 minute)

- a. *Today we are going to build on what we discussed last time by discussing your activities, and revisiting the SOBER breathing exercise.*
- b. *What questions or thoughts do you have about our last session?*
- c. If the participant missed the previous session , take a few moments to inform them of the information they missed.

5. Goal Setting Exercise (5 minutes)

- a. Have completed "Goals Worksheet" available from Session 1
- b. *To start today, I'd like to revisit your goals from session 1.*
- c. Restate Goals
 - i. *During session 1, you mentioned that this was your primary goal:*
 1. (read their primary goal from worksheet)

2. *Has this goal changed?*
 3. *Have you had the opportunity to work towards this goal in the past week?*
 - a. "No" is an acceptable answer.
 - b. Normalize that their goal right now may be "survival" and that's ok
 - d. Benefits and Barriers
 - i. *Let's talk more about the goal you identified.*
 1. *What would be the benefits of achieving this goal?*
 2. *What do you think might get in the way?*
 - ii. A goal that may seem completely appropriate may have some unforeseen barriers
 - e. Tracking progress and organizing activities with an app or calendar:
 - i. *Finally, I would like to ask you how you keep track of what activities you have planned?*
 - ii. *Do you use any sort of calendar?*
 1. *Some people find it helpful to write down activities in your calendar ahead of time.*
 - a. *What do you think about this?*
 2. If they are agreeable:
 - a. *Do you like a written calendar or use of a device, like a smartphone phone?*
 - b. Briefly summarize their thoughts on this (example: ok, so you might consider using the calendar on your phone to keep track of your activities).
6. Substance Free Activity: Identifying Activities (7 minutes)
- a. Have participant's completed Substance Free Activities Worksheet (from Baseline Assessment) available
 - b. Orient participant to topic
 - i. *Let's move to a new subject now.*
 - ii. *Many people who decide to make a change in their drug use find that developing other ways of having a good time, in order to fill the void left by drug or alcohol use, is a crucial part of their recovery.*
 - c. Review their answers to the substance free activities worksheet
 - i. *When you enrolled in the study, you completed a list of substance free activities that you enjoyed or found important to your recovery*
 1. *These are the activities you ranked the HIGHEST*
 - a. *Which of these activities/hobbies do you enjoy the most?*
 - b. Write down activities participant enjoys the most
 2. *What do you like about _(the activities they mention) _____ ?*
 - a. Talk through a few activities, focusing on exercise, socializing with non-users, and goal-directed, creative activities.
 3. *What are some of the reasons you want to focus on _(the activities they mention) _____ ?*
 - a. Talk through each activity they listed (limit this to 5 activities or less)
 4. *What are some of the things that could get in the way of enjoying these activities?*
 - a. For people who report few enjoyable activities help them to problem solve how they could access more activities.

7. Increasing Substance Free Activities (7 minutes)

a. Orient participant to topic

- i. *Now let's talk about taking some steps to increase your drug free activities.*
- ii. *Your preferred activities are _____ (list from above).*
 1. *What are some realistic steps you can start to take to implement this into your life more often?*
 2. *How would _____ activity fit in with your recovery plan?*

b. Tell them what you found for them

- i. *Great! To help you learn about some of these activities you mentioned last week, I have put together some information on how you can get involved in some of these activities in your community.*
 1. Encourage the participant to ask questions and take a few moments to explain the specific resources you provided (e.g., "You talked a lot about spending time with animals as a helpful tool in your recovery. Did you know that the Humane Society of Memphis is always looking for volunteers or foster homes for animals? Here is their information."
 - ii. *What are your thoughts in contacting one or two of these places next week (or doing these activities)?*
 1. Write down plan on the Session 2 Substance Free Activities Plan worksheet.
 2. If the participant does not express any motivation to incorporate substance-free activities into his/her life, the interventionist should focus on fostering ambivalence in the participant about his/her current time allocation. The interventionist should explore with the participant the pros and cons of continuing to allocate his/her time in this manner.
 3. The interventionist could also try to help the participant in considering more long-term goals if they are ambivalent with short-term.
 4. If there are barriers to participating in the substance free activities, the interventionist should help the participant problem solve ways to get involved in said substance-free activities.

c. Pleasant Activities Worksheet

- i. *Give worksheet to participant.*
- ii. *Lots of folks are having trouble finding ways to manage their stress during COVID. Here is a handout with a list of relaxing activities people can do at home.*
- iii. *Some of these may work for you, others may not. It is really to help you identify some strategies you can use, even when life isn't normal.*

d. Wrap Up

- i. *It sounds like you've put a lot of thought into how you would like to use your time. We can continue to talk about this next time.*
- ii. *I am going to send you this worksheet after our session today.*
- iii. *Send to participant following session*

8. Mindfulness-Based Adherence Promotion Intervention (5 minutes)

a. *Before we wrap up our time together today, let's talk a little more about the SOBER acronym we discussed last time. How has SOBER been working for you?*

- iv. *Remind the participant of the SOBER acronym if needed (Stop, Observe, Breathe, Expand, and Respond).*

9. Wrap-Up (1 minute)
 - a. *We covered a lot today during our session. Do you have any questions for me?*
 - b. *Let's schedule our next session together.*
 - c. Provide participant with date and time of session.

What to send to participant after Session #1:

1. Completed "Substance Free Activities Plan Worksheet"
2. Gift Card for completed assessment

Upload into Database after Session #1:

1. Completed "Substance Free Activities Plan Worksheet"

2. Session 2: Substance Free Activities Plan Worksheet

Substance Free Activity	Steps to start this activity

Psychosocial Intervention Session 3 (41 minutes with assessments):

Session Prep:

- Have participant's Substance Free Activities Plan Worksheet available from session 2.

1. Introduction (1 minute)
 - a. Getting Permission to Record
 - b. *Hi _____. Is this still a good time for us to do our next session together? Do I have your permission to record this session? Thank you!*
2. Assessment (10 minutes)
 - a. Complete session three assessment forms in FileMaker.
 - b. *Because you finished your assessment, I will mail you that \$25 gift card. Do you prefer Kroger or Walmart? Please allow 2-3 business days for it to arrive.*
3. Continue to Build Rapport (2 minutes)
 - a. *How have you been doing since we last spoke?*
 - a. Wait for participant to answer.
4. Orientation to Session (1 minute)
 - a. *Today, we are going to review the opioid-free activities you've been trying, and have a discussion about the deeper meaning of the SOBER breathing exercise.*
 - b. *What questions or thoughts do you have about our last session?*
 - c. If the participant missed the previous session , take a few moments to inform them of the information they missed.
5. Substance Free Activity Session Review (5 minutes)
 - a. *Last time, we talked more about the hobbies/activities you would like to try. What steps were you able to take towards starting the activities you mentioned?*
 - i. Allow the participant time to reflect and discuss the resource guide from the last session .
 - b. *Since _____ is a really important activity to you, what are some things that you can do to make progress towards this goal?*
 - i. Possible questions you might ask:
 1. *What would be the benefits of achieving these goals?*
 2. *What do you think might get in the way?*
 3. *How will you know if your plan is working?*
 4. *How will you know if you are getting off track? What steps would you take to get back on track?*
 - c. Summarize the goals/plans to the participant has for implementing substance-free activities.
 - i. *So you still want to try _____, but it turns out it costs too much to join the gym. So instead, you're thinking about _____. Does that sound right?*
6. Mindfulness-Based Adherence Promotion Intervention (20 minutes)
 - a. Orientation
 - i. *Let's spend a few minutes today talking specifically about the SOBER acronym.*
 1. *S is for Stop and see what happens*

2. *O is for Observe physical sensations and emotion regulation changes in the body*
 3. *B is for Breathe by deliberately bringing attention to the breath*
 4. *E is for Expand your awareness of the situation*
 5. *R is for Respond mindfully*
 6. *These last two letters are very important to practice but can sometimes be a little more challenging to understand. Let's talk about it.*
- b. Surf the Urge
- i. *Sometimes in the moment urges or moods can feel overwhelming – does that sound familiar? Our natural tendency is to give in to momentary urges and maybe in the past we have used alcohol or drugs to cope with urges, but we do have a choice. We can learn to “surf the urge” of a trigger to ride out cravings, urges, and triggers as they come up.*
 - ii. *Let's practice this now.*
 - iii. *I want you to imagine a situation that you are currently dealing with, maybe something recent that you found triggering. This doesn't need to be the most difficult situation you can think of, but one that is difficult or challenging for you.*
 1. For those who are currently distressed, no need to elicit a trigger
 - iv. *Do you have something in mind?*
 - v. *OK, let's walk through the steps.*
 1. **Stop:** Just take a moment to stop your immediate urge to react.
 2. **Observe:** Take a moment to really assess what you're feeling. Notice your emotions. Also, notice how your body feels during this time.
 - a. Also notice any thoughts that are coming up.
 3. **Breathe:** Take at least three deep and slow breaths to ride the wave of your trigger. Allow yourself to focus on the rhythmic breathing. You don't need to change your breathing, just notice it.
 - a. Take a minute to breathe with the participant in through their nose and out through their mouth slowly.
 - b. You might notice your mind wandering. That's ok, just bring it back to the breath.
